unsafe; 2) psychiatric worsening, such as emergence of depression (HamD score >17), psychosis (HamD item 22 >3), or of other significant psychiatric symptoms such as suicidality (HamD item 15 > 3), culminating in a CGI score > 6 for two consecutive weeks; 3) substance abuse worsening as assessed by clinicians on the research team during weekly visits, as evidenced by a CGI score >6 for two consecutive weeks; 4) emergence of hyponatremia during the study as indicated by a sodium concentration < 133 mEq/L or early symptoms such as asthenia, fatigue, nausea, vomiting, and weakness; 5) missing one week of supervised clinic-based administration of IN oxytocin or placebo.

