
3.3 Compensation and data management.

For phase 1, control participants will receive \$150 for their participation; cocaine-dependent patients will receive \$20/day, or will receive \$150 if they complete the whole week. [During phase 2, cocaine-dependent patients accumulate vouchers for completing all study procedures (Bringing home bottle, assessments, study visits).] Each visit with all study procedures completed will earn them \$5. They can also earn \$20 for each week of consecutive and complete participation. Transportation costs are covered (\$5/visit). Total earnings can reach \$450. StudyTrack, a software system for clinical trials will be used for data management.

3.4 Statistical Analysis:

3.4.1. Outcome measures: PHASE 1: **Primary outcomes:** 1) secretion of ACTH (continuous measure of area from the concentration-time curve (AUC) using trapezoid method, pg/mL/min). 2) subjective rating of cocaine craving, stress, depression, anxiety (continuous) 3) difference in ACTH secretion between IN DDAVP (day 1) and IN OT prior to IN DDAVP (day 2) (continuous measure); 4) difference in subjective rating of cocaine

craving, stress, depression, anxiety between IN VP (day 1) and IN OT prior to IN DDAVP (day 2; continuous, controlled for last day of use before entering Phase 1); **PHASE 2: Primary outcome:** 1) maximum number of consecutive abstinent days (continuous measure) ; **Secondary outcome:** 1) cocaine using days (continuous). **Covariates/Predictor Variables:** demographics, age, gender; cocaine data (TLFB, 30 days; IN vs. smoked).

3.4.2. Sample size: In PHASE 1, we will enroll a total of 100 participants: 1) Cocaine group (COC): Cocaine-dependent patients seeking treatment (n=50); 2) Control group (CON): Healthy matched controls (n=50), each matched demographically (see 3.1.1). In PHASE 2, we will randomize the 50 COC patients into two groups: 1) Oxytocin group (OT), n=25; 2) Placebo group (PBO), n=25. An independent statistician will perform, and an independent pharmacist will implement the randomization. Individuals will be stratified by route of cocaine use. The randomization will be balanced in blocks of random size 2 and 4 to prevent compromise of the blind.

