3.4.3. Intent to Treat/ Dropouts and missing data: All primary analysis will be on Intent-to-Treat (ITT) sample, i.e. all subjects from COC and CON groups in Phase 1 (50 per arm) and all subjects randomized to OT and PBO groups in Phase 2 (25 per arm). [In Phase 1, we expect little attrition. Measures as described (3.4.1) will provide usable data after 2 days of measurements. For phase 2, we anticipate an attrition rate of 30%, leaving approximately 18 completers per arm.] If a patient drops out during Phase 2, the maximum number of consecutive abstinent days achieved in the trial will be considered as primary outcome. The inferences from analyses with missing data are considered valid provided that they are "missing at random" (Little and Rubin 1987). One can assume either parametric or semi-parametric models for missingness (Diggle and Kenward 1994; Kenward 1998; Liu et al 1999; Rotnitzky et al 1998). Inferences from various models of missingness provides a measure of the efficacy estimate from each models.

3.4.4. Significance testing and preliminary analyses: All tests for main effects will be performed at two-tailed significance $\alpha=5\%$. Before performing specific analyses (described below), we will examine all variables for outliers and normality. Demographic variables (ethnicity, gender, age) and baseline measures in the groups will be described in terms of means, standard deviations, proportions and 95% confidence intervals. The covariates (Section 3.4.1) will be included if they are found to affect outcome measures.

Hypotheses:

Primary Aim 1 [Phase 1]: The goal of primary aim 1 is to investigate the effect that both IN DDAVP and OT have on stress sensitivity. **Primary Aim 1a, hypothesis 1:** IN DDAVP will be associated with greater secretion of ACTH and subjective ratings in cocaine dependent patients compared to control patients. **Primary Aim 1b, hypothesis 2:** IN OT treatment will significantly reduce the secretion of ACTH and subjective ratings associated with IN DDAVP in cocaine dependent patients compared to control patients. The differences based on the outcomes specified in hypotheses 1 and 2 between the subjects in COC and CON groups will be examined using parametric or non-parametric matched sample test.

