Primary Aim 2 [Phase 2]: The goal of primary aim 2 is to investigate the effect of OT on cocaine use after abstinence induction. **Primary Aim 2, hypothesis 1:** Cocaine-dependent patients receiving IN OT will display significantly more days of consecutive abstinence after abstinence induction compared with IN placebo at the end of the study. The effect of IN OT treatment (based on groups) on the primary outcome (maximum number of consecutive abstinence days for each patient) will be analyzed using generalized linear models (PROC GLIMMIX in SAS®) with main effect of randomization assignment (OT vs. PBO).

Secondary Hypotheses: We will examine the feasibility, safety, tolerability, and potential efficacy of IN OT for relapse prevention in cocaine dependence. 2.1): Cocaine-dependent patients receiving IN OT who complete all 6 weeks of phase 2 will tally fewer cocaine using days than placebo patients who complete all 6 weeks. 2.2): Cocaine-dependent patients receiving OT who relapse will tally fewer cocaine using days than patients receiving placebo who relapse. Regression analysis will be implemented using those who complete (2.1) and those who relapse (2.2) to test the effect of OT on the secondary outcome (cocaine using days).

Exploratory Aims: We will investigate a) if the acute reduction in stress sensitivity with IN OT in Phase 1 or at the end of Phase 2 (repeat IN DDAVP challenge) is associated with a greater number of days of continued abstinence from cocaine in Phase 2; b) if there are gender effects on the primary outcomes.

Power Analysis: **Primary aim 1:** With 50 cocaine dependent subjects and 50 matched controls, we have 50 matched pairs which give us at least 80% power to detect a significant difference between groups using 2-sided hypothesis test at a 5% level of significance for an effect size $\geq .41$. This is considered a small/medium effect size (Araya et al., 2006; Simeon et al., 2011), which are reasonable to expect based on the existing literature. **Primary aim 2:** In Phase 2, we randomize 50 participants into 2 groups (25 in PBO and 25 in OT). The comparison will achieve at least 80% power (testing 2-sided hypothesis of difference at 5% significance) when detecting an effect size ≥ 0.8 . This is a medium effect size that we based on existing relapse studies in cocaine dependence (Back et al., 2010).

Primary outcome:

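### Hypothesis 2.2 compares a raw count of cocaine-using days among relapsers with unequal follow-up and no denominator, so unequal removal between arms can create or mask a difference in use

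*SAP*

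**What the plan says.** SAP 3.4.1 gives the Phase 2 secondary outcome as "cocaine using days (continuous"). Under Secondary Hypotheses, 2.1 is limited to patients "who complete all 6 weeks of phase 2", which fixes follow-up at 42 days. Hypothesis 2.2 has no such condition: "Cocaine-dependent patients receiving OT who relapse will tally fewer cocaine using days than patients receiving placebo who relapse". For the analysis, the SAP says "Regression analysis will be implemented using those who complete (2.1) and those who relapse (2.2"). It names no offset, exposure time or follow-up covariate. The covariates listed in 3.4.1 are demographics and baseline cocaine data.

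Follow-up will vary. In SAP 3.4.3, "we anticipate an attrition rate of 30%, leaving approximately 18 completers per arm". Protocol, Study Procedures, Phase 2 item 12 removes patients who miss a week of medication. It also allows the investigator to remove them for "substance abuse worsening as assessed by clinicians on the research team during weekly visits", shown by a CGI score above 6 in two consecutive weeks. Criteria for Early Discontinuation and the section on minimizing risks repeat these grounds. After removal, item 12 promises only an attempt at end-of-study assessments, not a continued daily record.

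Three rules touch on missing information, and none settles 2.2:
- SAP 3.4.3 gives a specific dropout rule for the primary outcome, then a general missing-at-random statement that mentions various models of missingness.
- Protocol Phase 2 item 11 scores a missed visit as use, within the end-of-study responder rating.
- The closing Primary outcome section of the SAP treats a week with neither toxicology nor self-report as missing, for the weekly primary outcome.

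**The concern.** A count of events is comparable between patients only if they are watched for the same time. In 2.2 they are not, and one ground for ending observation is the outcome itself. A raw sum scores every unobserved day as a day without use. A patient using daily and removed at day 14 tallies at most 14 days; one using 3 days a week for all 42 days tallies 3 × 6 = 18. The heavier user has the better score.

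At arm level, a difference in removal feeds into the comparison of cocaine use. The result could show a difference where use is identical, or hide one where use differs. Because the plan does not say how days after removal enter the tally, the sign of the artefact depends on a choice left to the analyst.

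**Working it through.** **The plan's own figure.** 25 × (1 − 0.30) = 17.5, or about 18 completers per arm, as SAP 3.4.3 states. Attrition is not split by arm or by relapse status, and 2.2 has no sample size or power of its own. Everything below therefore rests on assumptions.

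**Illustration with identical use in both arms.** Phase 2 lasts 42 days (SAP). Assumed: relapse day uniform on 1 to 21 (mean 11); the relapse day is a using day; use on 50% of later days; removal 7 to 14 days after relapse (mean 10.5); a proportion p of relapsers removed.
- Not removed: 42 − 11 + 1 = 32 days from relapse; tally 1 + 0.5 × 31 = 16.5.
- Removed: 1 + 10.5 = 11.5 days from relapse; tally 1 + 0.5 × 10.5 = 6.25.
- Mean tally = 16.5(1 − p) + 6.25p.
- p = 20%: 13.2 + 1.25 = 14.45. p = 40%: 9.9 + 2.5 = 12.4.
- Spurious difference: (14.45 − 12.4) / 14.45 = 14%, favouring the arm with more removals.

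A simulation of 400,000 relapsers per scenario agrees: 15.5, 14.4, 13.4, 12.4 and 11.4 days for 10% to 50% removed.

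**Unobserved days counted as use.** Each removed patient gains 32 − 11.5 = 20.5 days.
- p = 20%: 14.45 + 0.2 × 20.5 = 18.55 (about 18.6). p = 40%: 12.4 + 0.4 × 20.5 = 20.6.
- The arm with more removals now looks worse.

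**Choice of denominator.** The mean number of days before relapse is 10.

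| | 20% removed | 40% removed |
|---|---|---|
| Observed days from relapse | 0.8 × 32 + 0.2 × 11.5 = 27.9 | 0.6 × 32 + 0.4 × 11.5 = 23.8 |
| Use per day from relapse | 14.45 / 27.9 = 0.518 | 12.4 / 23.8 = 0.521 |
| All observed days | 37.9 | 33.8 |
| Use per observed day | 14.45 / 37.9 = 0.381 | 12.4 / 33.8 = 0.367 |

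Dividing by all observed days leaves (0.381 − 0.367) / 0.381, or about 4%, because the days before relapse dilute the rate more in patients removed early. Counting from relapse gives about 0.52 in both arms. The tiny remainder arises because the relapse day is always a using day; without it the rates are 13.45 / 26.9 and 11.4 / 22.8, both 0.50.

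**Different assumptions.** Here there are 20 relapsers per arm, daily use probability Beta(2,3), removal on days 14 to 35, a two-sided 5% t-test and 3,000 replicates. The nominal rate of false significance in favour of oxytocin is 2.5%. Use is identical in both arms except in the last row.

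| Removed, oxytocin v placebo | Mean tally | False significance favouring oxytocin |
|---|---|---|
| 30% v 30% | 15.3 v 15.3 | 3.2% |
| 40% v 20% | 14.6 v 16.0 | 8.3% (11.0% if heavier users are removed more often) |
| 50% v 10% | 13.9 v 16.7 | 17.8% (30.9%) |
| 20% v 40% | 15.9 v 14.6 | 0.8% (6.2% favour placebo) |
| 50% v 10%, oxytocin use 25% higher | 17.1 v 16.7 | not applicable: a real difference is masked (proportions of days 0.515 v 0.415) |

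At 40% v 20% the gap is (16.0 − 14.6) / 16.0, about 9%. Counting all later days as use reverses it here too (21.6 v 19.5).

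**The case against.** A reader might infer that 2.2 is biased towards whichever arm loses more patients, or that a harmful treatment would show fewer using days. The documents do not support either as a general statement.
- Protocol Phase 2 item 11 scores missed visits as use. It sits in the responder rating and is not extended to days after removal, but it leaves open a reading under which the bias runs the other way.
- With equal removal there is no bias between arms, and no attrition by arm is given.
- In the harm scenario above, extreme imbalance still left oxytocin with slightly more days: harm was masked, not inverted.
- That counting stops soonest in the heaviest users is inference. Removal for worsening use is discretionary and needs two consecutive weeks of high CGI scores, and the 30% attrition is not attributed to use.

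SAP 3.4.3 is also not confined to the primary outcome, since its missing-at-random statement is general. But it does not define how unobserved days enter a tally. Finally, 2.2 is a secondary hypothesis with no power claim, and the SAP's closing section reports only the primary outcome, in 26 randomised patients (15 and 11). That limits the weight of the point and means the 20 relapsers per arm assumed above exceed what was available. None of this supplies the missing denominator.

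**Conclusion.** The concern holds in conditional form. Hypothesis 2.2 as written compares a count that depends on length of follow-up, and the plan expects follow-up to differ between patients. If removal differs between arms, the tally is distorted, and the direction depends on an unstated rule for days after removal. At 20% versus 40% removed, the illustrative artefact is 14% (14.4 v 12.4 days), or about 9% with later removal; counting unobserved days as use reverses it (18.6 v 20.6). These sizes rest on assumed relapse timing, use rates, removal timing and imbalance, none of which the documents give. The change should be made, with the modest priority of a secondary hypothesis.

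**What to change.** In the SAP, define the relapse day and analyse 2.2 as use per observed day from relapse onward. Either use a count model with the log of post-relapse days of known status as offset, or the proportion of those days with use. The proportion is the safer default if heavier users leave earlier, because a Poisson fit pools days and gives patients removed early less weight. Do not use all observed days as the denominator, since that leaves about 4% of artefact in the illustration. Report days observed by arm, and add a sensitivity analysis that counts unobserved days to day 42 as use. A rate assumes that observed days represent unobserved ones, so the two results should be read together.

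Describe 2.2 as a non-randomised comparison: it conditions on relapse, which occurs after randomisation, and no denominator cures that. As primary results already stand in the SAP, label the change as made after they were known.

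The cost is a few SAP sentences and slightly lower precision for patients with short follow-up. The TLFB already gives day-by-day use, so no new data are needed.

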## Specific Aims and Hypotheses

### Specific Aims and Hypotheses

**Primary Aim 1 [Phase 1]:** The goal of primary aim 1 is to investigate the effect that both IN DDAVP and OT have on stress sensitivity. *Primary Aim 1a, hypothesis 1:* IN DDAVP will be associated with greater secretion of ACTH and subjective ratings in cocaine dependent patients compared to control patients. *Primary Aim 1b, hypothesis 2:* IN OT treatment will significantly reduce the secretion of ACTH and subjective ratings associated with IN DDAVP in cocaine dependent patients compared to control patients. The differences based on the outcomes specified in hypotheses 1 and 2 between the subjects in COC and CON groups will be examined

using parametric or non-parametric matched sample test.

**Primary Aim 2 [Phase 2]:** The goal of primary aim 2 is to investigate the effect of OT on cocaine use after abstinence induction. Primary Aim 2, hypothesis 1: Cocaine-dependent patients receiving IN OT will display significantly more days of consecutive abstinence after abstinence induction compared with IN placebo at the end of the study. The effect of IN OT treatment (based on groups) on the primary outcome (maximum number of consecutive abstinence days for each patient) will be analyzed using generalized linear models (PROC GLIMMIX in SAS®) with main effect of randomization assignment (OT vs. PBO).

**Secondary Hypotheses:** We will examine the feasibility, safety, tolerability, and potential efficacy of IN OT for relapse prevention in cocaine dependence. 2.1): Cocaine-dependent patients receiving IN OT who complete all 6 weeks of phase 2 will tally fewer cocaine using days than placebo patients who complete all 6 weeks. 2.2): Cocaine-dependent patients receiving OT who relapse will tally fewer cocaine using days than patients receiving placebo who relapse. Regression analysis will be implemented using those who complete (2.1) and those who relapse (2.2) to test the effect of OT on the secondary outcome (cocaine using days).

**Exploratory Aims:** We will investigate a) if the acute reduction in stress sensitivity with IN OT in Phase 1 or at the end of Phase 2 (repeat IN DDAVP challenge) is associated with a greater number of days of continued abstinence from cocaine in Phase 2; b) if there are gender effects on the primary outcomes.

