- 2: On the days when patients do not attend the clinic, they will be asked to administer the randomized medication from an "at-home" bottle. They will be asked to bring the bottle at each visit to the clinic. In a single-blind fashion, it will be weighed as a measure of compliance. The metered bottle delivers 4 IU/0.1cc or per puff. Each daily dosing requires 6 puffs, or 0.6cc. The weight of each puff or 0.1 cc is approximately 0.1g. Hence, for each at-home insufflation, the bottle weight is expected to change by 600 mg. The expected change in weight will be plotted against the recorded change in weight, and this will be used to estimate at-home compliance.
- 3: At each visit, vital signs are recorded, and an inquiry is made about adverse events. The Time-Line-Follow-Back is completed to review drug use by calendar date. This allows a day-to-day review of reported drug use for each day of participation.
- 4: At week 2, 4, and 6, a thorough medical review will be carried out to ensure patient safety. This will include a review of systems, with a focus on lethargy, fatigue, nausea, and weakness, which are the usual symptoms of hyponatremia. Although the risk is remote, hyponatremia would be the major metabolic complication that could arise from intranasal oxytocin. Of note is the fact that it has been reported when oxytocin is used in the induction of labor with continuous intravenous infusion (Pitocin, PDR, 2014), a condition vastly different from those of this study. A blood draw will be done to monitor electrolytes and

---

blood counts. For women, a urine pregnancy test will also be done. Detection of pregnancy ends participation in the study.

5: Self-reports that will be completed weekly at one of the visits: Perceived Stress Scale, Cocaine Craving Scale.

6: The vital sign form, the review of system form (including blood results) will be dated and will refer to a calendar date of the clinical trial week it was performed to ensure proper recording.

7: At one of the visit, patients will meet with a research psychiatrist to review participation, whether progress or regress is being made, and to complete clinical ratings that will include a Substance Use Inventory, the Clinical Global Impression scale, a medical review, and completion of all clinical notes. All these forms are dated. These are then recorded in the clinical trial week form that corresponds to the calendar dates for that week.

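### Cocaine-using days, the only Phase 2 secondary outcome in SAP 3.4.1, is tested only in completers and in relapsers; no comparison of all randomised patients is planned

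*SAP*

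**What the plan says.** SAP 3.4.1 gives a single secondary outcome for Phase 2: "1) cocaine using days (continuous"). Two hypotheses concern it, worded alike in the SAP (Secondary Hypotheses, after 3.4.4) and in the protocol (Specific Aims and Hypotheses). Hypothesis 2.1 compares the arms among patients who finish the six weeks. Hypothesis 2.2 reads: "Cocaine-dependent patients receiving OT who relapse will tally fewer cocaine using days than patients receiving placebo who relapse". The analysis sets are named outright: "Regression analysis will be implemented using those who complete (2.1) and those who relapse (2.2").

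SAP 3.4.3 sets the general rules. On the analysis set: "All primary analysis will be on Intent-to-Treat (ITT) sample". On a patient who drops out in Phase 2: "the maximum number of consecutive abstinent days achieved in the trial will be considered as primary outcome". Neither sentence mentions using days. The closing Primary outcome paragraph of the SAP analyses the primary outcome only and reports nothing on using days.

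**The concern.** Completing and relapsing are both settled after randomisation and can both be affected by treatment. If the arm influences who completes or relapses, and membership is related to use, a comparison within either group is no longer a randomised one. If the arm does not influence membership, the completer result is valid for completers but may still differ from the effect in everyone randomised.

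Hypothesis 2.2 has a further difficulty. The hypotheses are introduced as concerning relapse prevention, yet a patient whose relapse is prevented leaves the comparison. The tally among those who remain mixes when relapse happened, how long the patient was observed afterwards, and how heavily the patient used. No adjustment for days observed is stated.

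At stake is the meaning of the secondary efficacy result: as planned, it cannot say whether being assigned to oxytocin changed cocaine use among the patients randomised.

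**Working it through.** **1. The SAP's completer figure.** Inputs from SAP 3.4.3: 25 per arm, and "we anticipate an attrition rate of 30%, leaving approximately 18 completers per arm". 25 × (1 − 0.30) = 17.5, rounded to 18, so the figure reproduces.

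**2. Patients outside hypothesis 2.1.** With the rounded figure, 2 × (25 − 18) = 14 of 50 (28%). Unrounded, 50 × 0.30 = 15 of 50 (30%).

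**3. Patients outside hypothesis 2.2.** This is everyone who does not relapse. The documents neither forecast that number nor define relapse. The two sets can overlap, since a completer may have relapsed, and a patient who leaves without relapsing is in neither.

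**4. Can completion be related to use?** Protocol, Study Procedures, Phase 2 item 12 removes a patient after one missed week of medication and lets the investigator remove a patient for worsening substance use (CGI above 6 for two consecutive weeks). Criteria for Early Discontinuation repeats both grounds. A link is therefore possible. No text says that relapse itself ends participation.

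**5. Precision.** Power ≈ Φ(d√(n/2) − 1.96). With d = 0.8, which the SAP gives for the primary outcome only and is assumed here:
- 25 per arm: Φ(2.83 − 1.96) = 0.81, which reproduces the SAP's statement of at least 80%.
- 18 per arm: Φ(2.40 − 1.96) = 0.67.

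The first figure carries over to using days only if they are available for dropouts.

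**6. Illustration for 2.1, all methods on the same scales.** Assumed: 42 days; logit-normal propensity to use (SD 1); placebo mean 28% of days (0.28 × 42 = 11.8); logit treatment effect −0.8; 30% placebo dropout on a day between 3 and 39. The log-odds of dropout rise by 0.5, 1 or 2 per SD of either pre-treatment severity or use under treatment. The offset method takes total using days over total observed days in each arm; the difference in rates is multiplied by 42. All results are unadjusted.

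| Comparison | Difference (days of 42) | Ratio |
|---|---|---|
| All randomised, full follow-up | −4.9 | 0.58 |
| Completers only | −3.1 to −4.6 | 0.54 to 0.65 |
| All randomised, observed-days offset | −4.2 to −4.8 | 0.57 to 0.60 |

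The offset comparison lies closer to the full-follow-up value on both scales, but it shrinks too. Where dropout follows pre-treatment severity alike in both arms, the completer figure describes a different population and is not biased for it.

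**7. Illustration for 2.2.** Two assumed models, neither with any effect on use after relapse:
- Relapse hazard halved (hazard 0.015 to 0.12 per day, no dropout, 24 scenarios): the oxytocin relapsers' tally is 0.1 to 1.1 days lower; among all randomised it is 1.2 to 2.4 days lower.
- Relapse reduced from 70% to 57%, with the tally after relapse depending on the patient's propensity and not on timing: the oxytocin relapsers' tally is 0.8 days higher; among all randomised it is 1.7 days lower.

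The relapser comparison changes sign between the models. The all-randomised comparison does not.

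**8. False positives with no drug effect** (nominal 5%, assumed inputs). With equal 30% dropout, 2.1 and 2.2 gave 3–6% and the offset model 5–7%. With unequal severity-related dropout (20% v 40%, or 15% v 45%), completers gave 7–10% and offset 5–6% at 25 per arm. With the 15 and 11 patients actually randomised, completers gave 5–7% and offset 5–6%.

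**The case against.** The case for leaving the plan alone has weight. The primary outcome also measures cocaine use and has an intent-to-treat comparison. The SAP forecasts the same attrition in both arms, and under equal dropout neither subset test is inflated; at 15 and 11 patients the offset model gains almost nothing in false-positive control. Observed days are themselves settled after randomisation, so the offset model answers a question about use per observed day. The reported median longest abstinence is 1.0 week in both arms, which may mean that most patients relapsed and that 2.2 omits few. The study calls itself preliminary and its primary results are in.

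All of that limits the size of the point, but none of it supplies the missing comparison. Nor does the other text that might be cited:
- The missing-data discussion in SAP 3.4.3 is not restricted to the primary outcome, but it does not change the analysis sets named for 2.1 and 2.2 or give a rule for using days.
- Phase 2 item 11 of the protocol names time to relapse and a responder rating. These are different measures, and no between-arm analysis is given for them.
- Item 11 also has scoring rules (missed visits recorded as days of use; use recorded when toxicology and self-report disagree). They sit in the responder rating and are not extended to using days. They do need to be addressed.

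A reader might infer that the subset tests are shown to be biased, or that 2.2 leans towards one arm. The documents do not support either. They give no dropout or relapse by arm, and steps 7 and 8 show that inflation and sign depend on what is assumed.

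**Conclusion.** The point holds as a missing randomised comparison and not as a demonstrated bias. Using days are to be tested only in groups formed after randomisation, and nothing in either document plans the comparison in all randomised patients. On the SAP's forecast, 14 to 15 of 50 patients fall outside 2.1; 2.2 omits an unstated number and cannot count a prevented relapse.

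That conclusion rests on the text alone. The simulations rest on assumed inputs and show only what could happen. The word only in the heading refers to SAP 3.4.1; the protocol names other secondary measures elsewhere. The primary outcome is unaffected and no using-days result is reported, so this is a modest point that is worth correcting because the correction is cheap.

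**What to change.** Make the test of cocaine-using days a comparison of all randomised patients by assigned arm. One suitable form is a count model allowing for overdispersion, with log observed days as offset, adjusted for route of use (the stratification factor in SAP 3.4.2) and baseline 30-day use. Both are among the SAP 3.4.1 covariates: "cocaine data (TLFB, 30 days; IN vs. smoked"). In addition:
- Report 2.1 and 2.2 as descriptive, non-randomised comparisons.
- State whether the two scoring rules in Phase 2 item 11 apply to using days, and show the result with and without missed days counted as use. Read the former as an extreme bound: with no drug effect and the unequal dropout of step 8, it gave 12–33% false positives at 25 per arm.
- Report dropout and observed days by arm, because any bias depends on them.
- Label the analysis post hoc, since primary results already appear in the SAP.

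The cost is one extra model on data already collected; of the Time-Line-Follow-Back the protocol says: "This allows a day-to-day review of reported drug use for each day of participation". The offset model estimates use per observed day and reduces informative dropout without removing it. If all dropout followed relapse and differed by arm (assumed), it gave 6.5–17% false positives, against 4–40% for completers and 13–51% for relapsers, and in some of those settings completers did slightly better. The analysis can no longer be prespecified.

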The primary outcome was maximum number of consecutive cocaine abstinent weeks. Cocaine use was determined using urine toxicology and TLFB self-report. In a given week, cocaine use was defined as positive if any urine toxicology tests or TLFB self-report was positive (regardless if urine toxicology was negative or missing). Cocaine use was defined as negative if both urine toxicology and self-report were negative or if urine toxicology was missing, the self-report was negative. Cocaine use status was defined as missing if both urine toxicology and self-report were missing. Wilcoxon rank-sum tests were used to examine differences in maximum number of consecutive cocaine abstinent weeks by medication group.

Twenty-six cocaine patients were randomized to 6 weeks of Oxytocin (n=15) or Placebo (n=11). The median (IQR) of the maximum number of consecutive abstinent weeks was 1.0 (1.0 to 1.0) for the OT group and 1.0 (1.0 to 2.0) for the PBO group. The Wilcoxon rank-sum test was not significant, there was no effect of treatment arm on the maximum number of consecutive abstinent weeks ($W = 144.5, p = .67$).

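### The Phase 2 power figure is about right, but an effect size of 0.8 is labelled medium when it is conventionally large; separately, the conclusion of no effect does not follow from p = .67 in 26 patients

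*SAP*

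**What the plan says.** The SAP, Power Analysis, Primary aim 2, randomises 50 patients, 25 to each arm. It says "The comparison will achieve at least 80% power" ("testing 2-sided hypothesis of difference at 5% significance") "when detecting an effect size ≥ 0.8". The next sentence describes that value: "This is a medium effect size that we based on existing relapse studies in cocaine dependence". The effect-size metric is not named, no benchmark for the word medium is given, and no difference or SD in abstinent days stands behind 0.8.

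Section 3.4.3 keeps every randomised patient in the primary analysis and counts the run of abstinence reached before dropout as the outcome. Section 3.4.4 sets the level: "All tests for main effects will be performed at two-tailed significance" of 5%.

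The closing Primary outcome section reports 26 patients randomised (15 oxytocin, 11 placebo). The median maximum run of abstinent weeks was 1.0 in both arms, with interquartile ranges of 1.0 to 1.0 and 1.0 to 2.0. The Wilcoxon rank-sum test gave p = .67, and the text concludes that "there was no effect of treatment arm on the maximum number of consecutive abstinent weeks". It gives no estimated difference and no confidence interval.

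**The concern.** There are two separate points.

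First, the adjective misdescribes what the design can detect. A reader who knows the usual scale (0.2 small, 0.5 medium, 0.8 large) and takes the word at face value will think the trial was sized for effects around 0.5. It was sized for effects around 0.8.

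Second, the results text turns a non-significant test into a statement that treatment made no difference. With 26 of the planned 50 patients and no interval, the reader cannot see which benefits or harms remain compatible with the data. This pilot is meant to inform whether intranasal oxytocin deserves further study, so treating an inconclusive result as a negative one could close the question without evidence.

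**Working it through.** **Inputs.** Two-sided alpha 0.05, target power 80%, 25 per arm, effect size 0.8 (SAP, Power Analysis, Primary aim 2). All randomised patients analysed (3.4.3). Numbers randomised: 15 and 11 (SAP, Primary outcome). Assumptions: the effect size is a standardised mean difference d, which is the reading that returns the SAP's own power; a two-sample t test stands in for the planned generalized linear model with a treatment effect only; medium means d = 0.5.

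**Formulas.** Noncentrality λ = d × √(n₁n₂/(n₁+n₂)). Normal approximation: power ≈ Φ(λ − 1.960). The exact figure uses the noncentral t distribution with n₁+n₂−2 degrees of freedom. Detectable effect at 80% power (normal) = (1.960 + 0.842)/√(n₁n₂/(n₁+n₂)).

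**The SAP's figure, 25 per arm.** √(625/50) = 3.536.
- d = 0.8: λ = 2.828. Normal: Φ(0.868) = 80.7%. Noncentral t, 48 df: 79%.
- Patients needed per arm at 0.8: 2 × 2.802²/0.8² = 24.5, so 25 (normal); 25.5 by t.
- Detectable effect: 2.802/3.536 = 0.79 (normal); 0.81 by t.

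The stated figure therefore reproduces. A one-sided 5% test would give 87%, so the two-sided reading is the one that fits.

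**A conventional medium effect, 25 per arm.**
- d = 0.5: λ = 1.768. Normal: Φ(−0.192) = 42.4%. Noncentral t: 41.0%.
- Patients needed per arm for 80%: 2 × 2.802²/0.5² = 62.8, so 63 (normal); 64 by t, or 128 in total.
- Between the two, by t: 54.7% at 0.6 and 67.9% at 0.7.

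**The numbers randomised, 15 and 11.** √(165/26) = 2.519.

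| Quantity | Normal | Noncentral t, 24 df |
|---|---|---|
| Power at d = 0.8 (λ = 2.015) | 52.2% | 49.0% |
| Power at d = 0.5 (λ = 1.260) | 24.2% | 22.7% |
| Detectable effect at 80% power | 2.802/2.519 = 1.11 | 1.16 |

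These figures use the planned effect and not the observed one, so they are not the circular kind of post-hoc power. The reported test was a rank-sum test; simulated with normal data it gives about 46% at 0.8 and 21% at 0.5. The real outcome is a short, heavily tied count of weeks, so the figures for 15 and 11 are a guide to the order of size only.

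**The case against.** The strongest reply is that nothing is miscalculated. The SAP makes one numerical claim, about 80% power at 0.8, and it holds. It claims no power at 0.5, and it prints 0.8 next to the adjective, so a statistician can see what the design detects. The 0.2/0.5/0.8 scale is an outside convention, and medium might mean typical of the cited relapse literature. Much of this stands: the error is one of labelling and missing justification, and the documents do not show that 0.5 was the right planning effect. But they do not define medium in any other way, and they give nothing in days that would let a reader judge 0.8.

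Four stronger readings are tempting, and the documents do not support them.
- *The claimed power is absent.* It is not; the stated pair reproduces within rounding.
- *The SAP contradicts itself by calling 0.41 small/medium in the Primary aim 1 statement.* That value is for 50 matched pairs and is standardised on within-pair differences. It is on a different scale from a two-group 0.8, so the two labels cannot be compared directly.
- *The 15 and 11 figures show that the power statement was wrong.* They reflect the randomisation of 26 patients and not 50. The results wording would need correction even if 0.8 had been called large.
- *The expected 30% attrition, about 18 completers per arm, cuts primary power to 64.5% at 0.8.* Section 3.4.3 keeps dropouts in the primary analysis with the run they achieved, so that figure does not apply to it.

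It can also be said that the results sentence gives p = .67 and calls the test not significant. It does, but it then goes on to assert that there was no effect, without an interval.

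**Conclusion.** The point holds as two limited corrections. The planned design has about 80% power for a large effect (79% by t, 81% by normal approximation, detectable effect 0.81) and about 41% for a conventional medium one. The calculation stands and the label should change. Separately, a non-significant test in 15 and 11 patients, with about 49% power at the planned 0.8 and a detectable effect of about 1.16, is inconclusive and does not show absence of effect.

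This rests on reading the effect size as a standardised mean difference, on 0.5 as the meaning of medium, on the t test as a stand-in for the planned model, and, for the last figures, on carrying the planned 0.8 over from days to weeks. The source cited for 0.8 could not be checked.

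**What to change.** **Power Analysis, Primary aim 2.** Restate as: *effect size 0.8 (large); power about 79% at 0.8 and 41% at 0.5; minimum detectable effect 0.81*. Name the metric, and give the difference in abstinent days and the SD from which 0.8 was derived.

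**Primary outcome results.** Replace the no-effect statement with: *no statistically significant difference was detected*. Report an estimated difference with a 95% confidence interval from a method that handles heavy ties, for example a bootstrap interval for the mean difference in weeks, or the probability of superiority with its interval. A Hodges-Lehmann interval suits these tied week counts poorly, and it does not convert to a standardised difference. State that with 26 patients the trial had low power even for the planned effect.

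**Cost.** Wording, one sentence of justification and one extra interval from data already in hand. The stated sensitivity becomes less favourable. No sample size, test or analysis set changes.
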